### 1.7. Statistical considerations:

With 250 women, the study will have 80% power, with an  $\alpha=0.05$  to find a mean decrease in GLS/GLSR of at least 2.5%.

The analysis plan is divided into three parts. In the first part a descriptive analysis of the data is done. Differences in biomarkers between unexposed and paired exposed groups (e.g. right vs. left-sided breast RT) at different time points are analysed to generate preliminary hypotheses on effects of RT on the heart. To investigate the time course of continuous variables extracted from ECHO-ST, CT or MRI measurements, mixed regression models are used. In the second part (anatomical) changes in cardiac biomarkers are correlated with dose distribution data. In the third part of the analysis multivariable Normal Tissue Complication Probability (NTCP) models are constructed. An integrative clinical-biological risk score is developed for individual risk prediction.

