##### **Non inclusion criteria:**

- Male breast cancer patients
- Neoadjuvant or adjuvant chemotherapy
- M1 disease (metastatic breast cancer)
- Medical history of coronary artery disease and/or myocardial infarction and/or atrial fibrillation
- Previous thoracic or mediastinal radiation
- Contraindications to injection of iodinated contrast such as allergy or renal failure
- Pregnancy or lactation

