## **Exclusion criteria**

- Atrial fibrillation detected during electrocardiogram before radiotherapy
- Abnormal echocardiography before radiotherapy defined as: LVEF<50%; longitudinal strain  $\leq$  -16%; longitudinal strain rate  $<$ -1%, and/or abnormal wall motion
- Presence of myocardial infarction detected during MRI before radiotherapy
- CTCA or cardiac MRI results before radiotherapy requiring revascularisation

▶ See CRF ELIGIBILITY in appendix for further details

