### 7.2. Before start of treatment protocol

About 1 to 2 weeks before the start of radiotherapy, during the visit for the RT planning-CT, women agreeing to participate in the study will give their signed written informed consent form and will then be considered as included. Cardiac MRI will not be mandatory for inclusion in EARLY HEART Study (in contrast with ECHO-ST, CT and BLOOD).

► See *CRF ELIGIBILITY*, *CRF CANCER*, *CRF planned RT* and *CRF CARDIOLOGY*, in appendix for further details

From this inclusion visit on, women's follow-up protocol will be realized. Before start of RT the following interventions will have to be performed:

- Cardiac imaging:
  - An electrocardiogram to detect any arrhythmia followed by an Automated 2D-speckle-tracking echocardiography (ECHO-ST) the most commonly used modality to evaluate myocardial dysfunction and a new technique of assessing myocardial deformation;  
► See *CRF ECHO-ST* in appendix for further details
  - Computed tomography (CT) by using both low dose non enhanced and enhanced CT scans to evaluate coronary artery lesions by assessing morphological information including plaques and stenosis of the arteries, and determination of the CAC score;  
► See *CTCA PROTOCOL* and *CRF* in appendix for further details
  - Cardiac magnetic resonance imaging (MRI) for the measurement of ventricular function, size of the two heart chambers, and wall thickness; tissue characterization by delayed enhancement; and pre-/post-contrast T1 mapping mapping and pre contrast T2 mapping of the left ventricle.  
► See *MRI PROTOCOL* and *CRF* in appendix for further details
- Circulating biomarkers (BLOOD) will be based on a panel of circulating classical and novel blood-based biomarkers (see 7.5 *Blood samples for biomarkers analysis* for further details)

Furthermore, toxicity will be assessed according CTCAE 4.03 and patient rated outcome

measures. ► See *CRF TOXICITY in appendix for further details*

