### 9.2. Sample Size

The sample size was based on a statistical power of 80%, an alpha-risk of 5%, the definition of the primary endpoint (a decrease in the global and segmental longitudinal strain or strain rate of at least 2.5%) and baseline measurements hypothesis (mean global longitudinal strain before RT : -16.5%  $\pm$  2.1% from Dalen et al, European Journal of Echocardiography : the Journal of the Working Group on Echocardiography of the European Society of Cardiology. 2010) Considering paired test for comparisons, but also possible lost to follow-up due to death or other reason, the inclusion of 250 women is necessary for EARLY-HEART study.

Centre	Recruitment rate per month	Total number of patients to recruit in 1 year
IRSN	4.2	50
UMCG	5	70
TUM-MED	4.6	55
CCUL	2.1	25
ICO	4.2	50
Total		250

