## Appendix

## Appendix

### CRF ELIGIBILITY

**Inclusion Number:** .....

**Date of the visit :** .....

**Date of Birth:** .....

➤ **Inclusion Criteria (check each point)**

- Female breast cancer patients
- Treated with primary breast conserving surgery for stage I-III invasive adenocarcinoma of the breast or ductal carcinoma in situ (DCIS)
- Age between 40-75 years at time of start radiotherapy
- WHO performance status 0-1
- Planned for radiotherapy alone to the breast with or without the lymph node areas
- Radiotherapy based on planning-CT scan using either 3D-CRT, IMRT, or VMAT/RapidArc
- Written Informed consent

➤ **Non Inclusion Criteria (check each point)**

- Male breast cancer patients
- Neoadjuvant or adjuvant chemotherapy
- M1 disease (metastatic breast cancer)
- Medical history of coronary artery disease and/or myocardial infarction and/or atrial fibrillation
- Previous thoracic or mediastinal radiation
- Contraindications to injection of iodinated contrast such as allergy or renal failure
- Pregnancy or lactation

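### The baseline strain exclusion lies 0.24 SD from the planning mean behind the 250, and the plan does not settle whether the 250 are counted before or after it

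*Combined protocol and SAP*

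**What the plan says.** **Sample size.** Section 1.7 says "With 250 women, the study will have 80% power" at alpha 0.05, and section 9.2 says "the inclusion of 250 women is necessary for EARLY-HEART study". The baseline input in 9.2 is "mean global longitudinal strain before RT : -16.5"%, with SD 2.1%. A paired test is assumed. The only attrition mentioned is loss to follow-up, through death or otherwise, with no rate. The SD of the change, the sidedness of the test and the scale of the 2.5% decrease (relative or in strain points) are not given.

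**Baseline exclusion.** Section 4 has one list headed "Non inclusion criteria" and a separate list of exclusion criteria. The second includes "Abnormal echocardiography before radiotherapy defined as: LVEF<50%; longitudinal strain" at or below -16%. The Local CRF ECHO-ST repeats this cut-off and says that the patient should then be excluded. The eligibility CRF covers the inclusion criteria and "Non Inclusion Criteria (check each point"), but not the imaging exclusions.

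**When a woman is included.** Section 7.2 says that women at the planning-CT visit "will give their signed written informed consent form and will then be considered as included". The baseline procedures run from that visit on. The same paragraph, however, contrasts optional MRI with ECHO-ST, CT and blood sampling, which it treats as required for inclusion. Section 5 describes the 250 as women treated with radiotherapy and assessed over the following two years. The monitoring plan in section 12.4 requires participants to meet no exclusion criterion.

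**Recruitment.** The 9.2 table gives monthly rates by centre and a column headed "Total number of patients to recruit in 1 year", which totals 250.

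**The concern.** A sample-size calculation and an eligibility rule should describe the same women. Here the exclusion threshold sits almost on the assumed population mean, so whichever way the inequality runs it would remove a large share of the population that the calculation assumes. Section 9.2 makes no allowance for this, and no screen-failure rate or replacement rule appears elsewhere.

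This matters because 80% at 250 is the plan's only power statement. If the 250 are counted at consent, the number who reach the paired analysis is neither stated nor planned for. If they are counted after baseline imaging, the number of consents, and so the accrual time, is unplanned.

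**Working it through.** **1. Reproducing the 250.** The stated inputs alone do not give it. Assume that 2.5% is relative (0.025 × 16.5 = 0.4125 points), a two-sided 5% test, and a within-woman correlation r = 0.5, so that the SD of change is 2.1 × √(2 × (1 − 0.5)) = 2.1.

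- n = (2.1 × 2.802 / 0.4125)² ≈ 204 (206 by the t-test).
- An assumed loss to follow-up of 18.4% gives 204 / 0.816 = 250.

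On this route the whole margin from 204 to 250 goes to follow-up loss and none is left for baseline exclusion. Other routes are possible: a one-sided test with r = 0.3 and 10% loss also gives 250. If 2.5% means absolute points, about 6 women suffice at r = 0.5 (8 by the t-test).

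**2. Share excluded.** Inputs: mean -16.5 and SD 2.1 (section 9.2), cut-off -16 (section 4; Local CRF ECHO-ST). Normality is assumed, as is that the planning mean and SD describe the consenting women.

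- z = (−16 + 16.5) / 2.1 = 0.238.
- P(GLS ≤ −16) = 0.594; P(GLS > −16) = 0.406.

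| | As printed (≤ −16 excluded) | Inequality reversed |
|---|---|---|
| Excluded | 59% | 41% |
| Kept of 250 consents | 250 × 0.406 ≈ 101 | 250 × 0.594 ≈ 149 |
| Consents for 250 kept | 250 / 0.406 ≈ 616 | 250 / 0.594 ≈ 421 |

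These counts come before the other baseline exclusions and before follow-up loss. If the true mean were −17, −18 or −19 (assumed, same SD), the reversed rule would keep 171, 207 or 231 of 250, and the printed rule 79, 43 or 19.

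**3. Power if the 250 are consents.** Two-sided noncentral t, before follow-up loss, with the SD of change and the target unaffected by selection:

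| Assumption | 250 analysed | 149 kept (reversed) | 101 kept (printed) |
|---|---|---|---|
| Relative 2.5%, r = 0.5 | 87% | 66% | 50% |
| Relative 2.5%, r = 0.7 | 98% | 87% | 71% |
| Absolute 2.5 points, r = 0.5 | about 100% | about 100% | about 100% |

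Selection on baseline also narrows the SD of change and shifts the kept mean. At r = 0.5, using the truncated SD gives 73% (reversed) or 57% (printed). Taking the 2.5% from the kept mean as well gives 80% or 47%.

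**4. Accrual if the 250 are eligible women.** The table's rates sum to 4.2 + 5 + 4.6 + 2.1 + 4.2 = 20.1 per month. If they count consents, 421 / 20.1 ≈ 21 months and 616 / 20.1 ≈ 31 months, against the stated 1 year. If they already count eligible women, 250 / 20.1 ≈ 12.4 months and this objection falls away.

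**5. Recruitment table.** Rate × 12 gives 50.4, 60, 55.2, 25.2 and 50.4; the printed totals are 50, 70, 55, 25 and 50. Only the UMCG row disagrees. The printed column does sum to 250. The rates give 20.1 × 12 = 241 because of that one row.

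**The case against.** The best reply is that the 250 are eligible women. Section 7.2 itself treats ECHO-ST and CT as required for inclusion, section 5 speaks of women treated and followed for two years, and section 12.4 allows no participant who meets an exclusion criterion. On that reading screening costs no power. This stands as a fair reading, but it does not remove the consent sentence in the same paragraph of 7.2, and it leaves the number of consents unplanned.

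Three stronger readings are tempting, and the documents do not support them:

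- **That the study is underpowered.** This would need the SD of change and the scale of the 2.5%. Neither is stated, and under some plausible values power stays at or above 80%.
- **That accrual stops at 250 consents.** No stopping rule is given and replacement is not barred. The plan is silent.
- **That the inclusion number on the ECHO-ST form shows that counting precedes imaging.** The eligibility CRF carries the same field while criteria are still being checked, so the number does not date inclusion.

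It can also be said that the planning mean may not describe these women. That may be so, but it is the plan's own input. The counts in step 2 show that at the other means tried the result still depends heavily on the direction of the inequality.

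**Conclusion.** The point holds as an inconsistency and an undefined count. The -16% exclusion and the -16.5% planning mean do not fit together: as printed, the rule excludes a woman at the planning mean, with no distributional assumption needed. The shares of 59% and 41% rest on normality and on the planning mean and SD applying to these women.

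What the 250 counts is left open. The consequence is either about 101 or 149 women remaining from 250 consents, with a conditional effect on power, or about 616 or 421 consents, with an accrual time that the 1-year figure does not cover if the table's rates count consents. A loss of power is possible but not demonstrated. The UMCG row is a single separate slip that needs no assumption and has no bearing on power. This should be fixed before the sample-size statement is relied on.

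**What to change.** 1. Reconcile the direction and value of the strain cut-off in section 4 and the Local CRF ECHO-ST with the planning mean in 9.2. This review does not say which is right.
2. In 9.2 and 1.7, state that the 250 are women who have passed all baseline exclusions, with screen failures replaced and not counted, and align the inclusion wording in 7.2. Alternatively, if 250 consents is fixed, restate the power for the expected evaluable number, giving the SD of change, the scale of the 2.5%, the sidedness of the test and the rate of follow-up loss.
3. Correct the UMCG rate or its total and, if the total changes, the 1-year figure.

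The cost is protocol and form wording, with no new procedure. The downside is more consents and longer accrual under the first option in item 2, or possibly a less favourable stated power under the second.

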### 9.3. Analysis plan

IRSN and UMCG will be in charge of main statistical analysis in close collaboration with other investigating centres.

The analysis plan consists of three stages:

#### *Stage I: Descriptive analysis*

Means, standard deviations, percentages, ranges and confidence intervals of 95 % are used to summarize:

- The questionnaire medical data;
- The 2D-speckle-tracking echocardiography (ECHO-ST) measurements including strain and strain rate.
- The Coronary computed tomography angiography (CT) measurements including mean number of coronary segments with plaques and/or stenosis, and CAC score (Agatston, Volume), total and per coronary artery;
- The MRI measurements include ventricular function, size of the heart chambers and wall thickness, tissue characterization by delayed enhancement and pre-/post-contrast T1 mapping of the left ventricle;
- The measurements of all biomarkers;
- Dose distribution to the several heart substructures including ventricles and coronaries arteries.

Paired non-parametric tests (Wilcoxon signed rank test to compare medians, McNemar and Bowker to compare paired proportions). The correlation between the different covariates will be investigated using the Spearman's rank correlation coefficient.

#### *Stage II: Radiation-induced Cardiovascular Changes Models (RCCM)*

The Radiation-induced Cardiovascular Changes Models (RCCM) aim to investigate the dose-

response relationships between 3D-dimensional dose distributions in cardiac substructures and cardiovascular changes in term of imaging and circulating biomarkers time-kinetics occurring in the 2 years after radiotherapy for breast cancer (before RT, 6 and 24 months after RT).

To investigate the time course of continuous variables extracted from ECHO-ST, CT or MRI measurements, mixed regression models are used since these longitudinal data present a hierarchical structure where serial measurements are nested within individuals over time. In this framework, a variable selection is possible by an AIC or BIC model selection or by incorporating a lasso or an elastic net penalty especially for the imaging and circulating biomarkers selection. To investigate some non-linear predictor effects, a fractional polynomial approach could be considered.

The radiation exposure could be included in this model by several ways: point wise dosimetric parameters (mean dose,  $D_x$  or  $V_x$ ), DVH reduction equivalent uniform dose (EUD) or through a functional data analysis approach by estimating a functional coefficient associated to a functional predictor (here the DVHs or the probability density function).

To exploit the richness of the longitudinal global or regional strain curves, a myocardial deformation analysis will be conducted using a functional mixed effect model to deal with the infinite-dimensional functional responses measured at multiple time points.

### *Stage III: NTCP and functional NTCP models (F-NTCP).*

In presence of cardiac toxicity outcome, a multimetric NTCP modelling is constructed through time-dependent covariates and time dependent coefficients Cox model.

The individualized risk estimation is calculated from an integrative clinical-biologic risk score obtained at the end of a variable selection process (lasso or elastic-net partial likelihood penalization for example).

The radiation exposure could be included in this model by several ways: point wise dosimetric parameters (mean dose,  $D_x$  or  $V_x$ ), DVH reduction equivalent uniform dose (EUD).

Using a time-dependent Cox regression performed in a functional data analysis way, a functional NTCP model (F-NTCP) will provide a volume-effect functional parameter which allows a risk weighting across the considered dose range and especially for the lowest one.

Furthermore, as a complementary approach for cardiovascular risk modelling, the cardiac imaging and circulating biomarkers will be integrated into a mechanistic model of cardiovascular disease, including atherosclerosis (Work package 4.3 Cardiovascular risk modelling, HMGU).

## 10. REPORTING ADVERSE EVENTS

This is a prospective observational cohort study in which radiotherapy and other oncologic treatments will be performed according to current standard of the participating centres without additional risks.

Serious adverse events related to blood samples or cardiac imaging exams are not expected. The subjects with possible abnormal findings are referred for further examination in accordance with normal procedures in each country.

Minor adverse events are those related to blood samples and cardiac imaging exams.

- Blood collection (pain at veins at the elbow, allergy to products used to clean the skin, hematoma)
- Echocardiography is based on the use of ultrasound. This is a non-invasive method of investigation, non-traumatic and painless. It can be repeated and there are no contraindications. It has not known side effects. It lasts about 15 minutes.
- The CT lasts about 20-30 minutes. The CT requires the injection of iodinated contrast with contraindications (renal failure, allergy). The injection of iodinated contrast material is made in compliance with the contraindications of the latter. The place of injection is done simply at the arm vein. Potential side effects of iodine contrast include flushing, and (mild) skin rash.
- For CT, patient is subject to a scanning X-ray beam. This examination is relatively simple, painless, and safe if one respects the contra-indications. The examination can be done as an outpatient without hospitalization. In terms of radiation dose, the latest techniques in cardiac CT achieve very low levels of radiation, equivalent to one to two years of natural background radiation (average of 2.4 mSv / year), considered acceptable for exam screening for which the radiation-induced risk should be minimal or nil.
- Nitroglycerine may be administered prior to the CT angiography, which is a safe and often used medication for patients with CAD. Side effects include flushing, headache and hypotension, and will not be given to patients with a low blood pressure, left ventricular outflow obstruction or using sildenafil or related medication.
- Betablockers may be used in patients with a fast heart rate before CT. Beta-blockers are used by many patients and regarded as safe. They should not be given to patients with hypotension or conduction disorders as described in the contra-indications to the study.
- MRI is based on magnetic field and radio waves. This examination is relatively simple, painless, and safe if one respects the cons-indications. The examination can be done as an outpatient without hospitalization. MRI is the safest of the advanced imaging techniques.

However, it is known that for certain patients who undergo MRI examinations, the experience may be associated with emotional distress, anxiety and claustrophobia, which could limit the consent of patients to participate in our study. MRI lasts about 45 minutes. This point must be considered in the design of the study by proposing additional MRI examinations as an option in the protocol (in contrast with blood collection, ECHO-ST and CT that would be mandatory).

- Cardiac MR including gadolinium (Dotarem 0.2 mmol/kg) enhancement will be performed. Potential side effects of gadolinium include brief headache, nausea (feeling sick) and dizziness for a brief time following the injection. Allergic reactions are rare.

The investigator will inform the patients and the reviewing accredited Medical research ethics committee if anything occurs, on the basis of which it appears that the disadvantages of participation may be significantly greater than was foreseen in the research proposal. The study will be suspended pending further review by the accredited Medical research ethics committee, except insofar as suspension would jeopardise the subjects' health. The investigator will take care that all subjects are kept informed.

## **11. ETHICAL CONSIDERATIONS**

### **11.1. Regulation statement**

This study will be conducted in accordance with the Declaration of Helsinki (amended at the 64th WMA General Assembly, Fortaleza, Brazil, October 2013) (appendix 1) and in accordance with the principles of 'Good Clinical Practice' and the Medical Research Involving Human Subjects Act (WMO).

### **11.2. Recruitment and consent**

The study aims and procedure will be explained orally and in writing in a study information leaflet to each eligible patient, by each specific participating centre. All study patients are also informed that she will be part of a larger European study.

The patients will have ample opportunity to ask questions they might have and they will have 48 hours to consider the implications of the study before deciding to participate.

Patients consent will be noted on an informed consent form compliant with the local and ethical regulations.

If during the study the patient for whatever reason no longer wishes to participate, she can withdraw her consent at any time.

All countries involved in the multicentre study will contact the local ethics committee and are familiar with the national procedures. Prior to the start of the study, the protocol has to be approved

by the medical ethics review committee of the participating institution. Approval will be indicated in writing with reference to the final protocol number and date.

### **11.3. Objection by minors or incapacitated subjects**

Not applicable.

### **11.4. Benefits and risks assessments, group relatedness**

Participation in this study does not involve any additional risk to patients, besides the risk incurred by additional MRI and CT-scans. Patients will undergo 2 extra CT-scans. For CT, patient is subject to a scanning X-ray beam. The latest techniques in CTCA achieve very low levels of radiation (below 4mSv) , equivalent to one to two years of natural background radiation (average of 2.4 mSv / year), considered acceptable for exam screening for which the radiation-induced risk should be minimal or nil. Additionally, compared to the radiation dose of the treatment the dose of the extra CT scans is very low and the risks therefore are negligible and the burden low.

Participation in this study may have benefits. When cardiac imaging reveal severe abnormal findings, such as the presence of severe coronary artery disease which may require a revascularization or specific treatment due to the presence of a myocardial infarction, patients even in absence of symptoms will be excluded of the present study and referred to the cardiologist . In absence of severe coronary artery disease, all results of cardiac imaging will be blinded to the medical staff in order to avoid changes in medical treatment likely to mask effects of XRay radiation which the main objective of the present study.

